#### **8.2.4.2 Seizure Freedom**

The number and percentage of subjects with seizure-freedom (partial, all epileptic seizure) during the Evaluation Period will be summarized by study group.

## **9 SAFETY ANALYSES**

All safety analysis will be based on SS.

### **9.1 Extent of exposure**

#### **9.1.1 Study medication duration and total study medication duration in subject-years**

Duration of exposure to study medication is defined as the total number of days a subject is exposed to study medication and will be calculated as the date of last dose in EP0085 minus date of first dose in EP0085 plus one in days. If the last dose date on the Study Termination / Early Discontinuation page is missing the last dose date will be captured from the Drug Dosing Log CRF. Gaps in BRV treatment or days on the Drug Dosing Log CRF with unknown dosing and/or partial missing exposure date will not be subtracted from the total duration of exposure.

Total study medication duration in subject-years will be calculated as the total duration of exposure in days divided by 365.25.

The duration of exposure to study medication will be summarized by study group for all subjects in the SS and will be presented in a table by summary statistics.

The subject cumulative exposure duration will then be classified into one of the following categories:  $>0$  month,  $\geq 3$  months,  $\geq 6$  months,  $\geq 12$  month,  $\geq 18$  month,  $\geq 24$  months,  $\geq 36$  months,  $\geq 48$  months, and so forth in 12-month increments up to the maximum duration of

exposure and will be presented as the number and percentage of subjects in each duration category by BRV overall and by modal dose group. Percentages for BRV overall will be computed based on the Safety Set. Percentages for the modal dose group will be computed based on the number of subjects exposed overall or within each duration of exposure.

### **9.1.2 Study medication dose**

The total cumulative dose will be defined as the sum of the doses across all study days. The mean daily dose is defined as cumulative dose divided by total days on study medication.

The modal daily dose will be calculated across all study days on or after the day of first dose of BRV and up to and including the day of last dose of BRV. Modal daily dose is the most frequently taken daily dose during the study. In the event of a tie, the modal dose will be set to the lower of the tied doses. Modal daily dose will be categorized as follows:

Category	Definition
5 mg/day	<20mg/day
20mg/day	≥20mg/day to <50mg/day
50mg/day	≥50mg/day to <100mg/day
100mg/day	≥100mg/day to <150mg/day
150mg/day	≥150mg/day to <200mg/day
200mg/day	≥200mg/day

The mean daily dose, modal daily dose, and modal daily dose category will be summarized using descriptive summary statistics by study group.

A summary of each subject's exposure will be presented in a listing.

## **9.2 Primary safety variables**

### **9.2.1 Definition of treatment-emergent adverse events**

AEs will be classified as either pre-treatment or treatment-emergent. Pre-treatment AEs are defined as AEs which had onset prior to the date of the first dose of BRV in EP0085 study. Treatment-emergent AEs (TEAEs) are defined as AEs that had onset on or after the day of first BRV dose in EP0085 study. AEs with an incomplete onset date will be classified as TEAEs if the month and year of onset (when only the month and year are specified) is the same as the month and year of the first BRV dose or the year of onset (when only year is specified) is the same as the year of first BRV dose.

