### 2.2 Study variables

#### 2.2.1 Safety variables

##### 2.2.1.1 Primary safety variables

The primary safety variable is treatment-emergent adverse events (TEAEs).

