### 3.2.2 Relative day

Relative day will be calculated as follows:

- For days prior to the first dose of BRV, the relative day is the current date minus the date of first dose of BRV. The relative day prior to first dose will be Day -1.
- For days on or after the first dose of BRV and on or prior to the last dose of BRV, the relative day is the current date minus the date of first dose of BRV plus 1. The relative day of first dose will be Day 1.
- For days after the last dose of BRV, the relative day is the current date minus the date of last dose of BRV. The relative day will include a “+” to denote post treatment days (eg, the day after the last dose will be Day +1).

Relative day will not be calculated for partial or missing dates.

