## **4 STATISTICAL/ANALYTICAL ISSUES**

### **4.1 Handling of missing data**

No rule for handling of missing data will be applied for this LTFU study. Safety and efficacy variables will be analyzed as available. Days with missing information will be ignored in the calculation of the seizure frequency.

Since subjects may drop out from the study at different times, selected summaries will be presented by time interval.

Subjects participating in EP0118 while also enrolled in EP0085 will have missing data for seizure frequency and drug dosing while participating in the EP0118 study. As the duration of the EP0118 study will be short (3-7 days), no imputation for data missing due to participation in EP0118 will be performed. Subjects will be assigned the same dose in EP0118 as that assigned in EP0085 for the two weeks prior to the start of EP0118. As such, time during the EP0118 study will not be subtracted from the exposure calculations (eg, exposure will be from the start of BRV treatment in the EP0085 study until the date of last dose of BRV in EP0085).

For the calculation of variables related to seizure frequency, the dates during participation in EP0118 will be considered as not done for the purpose of efficacy analyses for EP0085 according to the Seizure Count form entry (eg, these dates will not be considered as days evaluated for seizure frequency).

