### **9.2.2 Summaries of TEAEs**

Pre-treatment AEs will be provided in a subject data listing; no summary of pre-treatment AEs are planned. Summaries will be for TEAEs and will be provided overall by combining Evaluation Period, Down-Titration Period, and Study Drug-Free Period unless otherwise indicated.

The following summary of TEAEs will be provided:

- Incidence of TEAEs – overview (overall and by study periods)

The following summaries of TEAEs will be provided by MedDRA SOC and PT:

- Incidence of TEAE (overall and by study periods)
- Incidence of TEAEs by safety time interval (overall)
- Incidence of TEAEs above reporting threshold of 5% of subjects (overall)
- Incidence of non-serious TEAEs above reporting threshold of 5% of subjects (overall)
- Incidence of TEAEs by maximum intensity (overall and by study periods)
- Incidence of TEAEs by relationship (overall and by study periods)
- Incidence of TEAEs leading to permanent discontinuation of study drug (overall)
- Incidence of treatment-emergent SAE (overall and by study periods)
- Incidence of treatment-emergent SAE by relationship (overall)
- Incidence of fatal TEAEs by relationship (overall)
- Incidence of TEAEs of special interest (overall and by study periods)
- Incidence of TEAEs requiring dose change (overall and by study periods)
- Incidence of TEAEs related to COVID-19 vaccination (overall and by study periods)

For by-study period summary tables, TEAEs will be attributed according to the onset date.

Three-month safety time interval will be used to summarize data up to and including the maximum duration of exposure to BRV. TEAEs which had onset prior to or on the date of the last dose of BRV are included in summaries by 3-month time intervals. A subject is included in a 3-month interval if the subject was receiving BRV at any time during that interval based on their duration of exposure to BRV (eg, a subject with exposure for 91 days is included in the time interval for Months 1-3 and Months 4-6). Summaries of AEs by 3-month intervals will include all subjects who are classified into each time interval as defined above as the denominator and TEAEs reported within the specific time interval according to the onset date as the nominator.

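### The SAP's rule for incomplete AE onset dates ignores the end date and has no branch for a wholly missing onset, so individual AEs can be misclassified in the primary safety variable

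*SAP*

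**What the plan says.** TEAEs are the primary safety variable (SAP 2.2.1.1). SAP 9.2.1 sets up two classes: "AEs will be classified as either pre-treatment or treatment-emergent". Both are defined by onset. For the first, "Pre-treatment AEs are defined as AEs which had onset prior to the date of the first dose of BRV in EP0085 study". For the second, "Treatment-emergent AEs (TEAEs) are defined as AEs that had onset on or after the day of first BRV dose in EP0085 study".

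For partial dates the section adds one rule, which begins "AEs with an incomplete onset date will be classified as TEAEs if the month and year of onset" and requires these to equal the month and year of the first dose. If only the year is known, it must equal the year of the first dose. The rule has no condition on the end date. It covers these two patterns only, and a wholly missing onset is not mentioned.

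SAP 4.1 provides no fallback: "No rule for handling of missing data will be applied for this LTFU study".

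Pre-treatment AEs are listed but not summarized (SAP 9.2.2), so the class decides whether an AE appears in any summary table.

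**The concern.** A partial onset date leaves it open whether an AE began before or after the first dose, and calling it treatment-emergent is a reasonable default. It stops being reasonable when the record itself answers the question. An AE that ended before the first BRV dose cannot have started on BRV, whatever its start day. The rule does not look at that information and assigns the AE to BRV.

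The second gap works the other way. The SAP intends every AE to fall into one of two classes, but both need an onset date. An AE without one belongs to neither, and no rule elsewhere places it. Read literally, the TEAE tables would omit it, although the SAP treats missing relationship as related (9.2.2.5) and missing intensity as severe (9.2.2.6).

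At stake is the accuracy of the TEAE counts. The direct enrollers matter most, because they were added to accumulate safety data (Protocol section 1) and are analyzed separately (Protocol section 12, SAP 3.6).

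**Working it through.** The plan states no figure to reproduce on this point. The check applies the rule literally to test cases and then works out who can be affected.

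**Step 1: test cases.** Suppose the first BRV dose is on 20 June 2020.

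| Recorded onset | Recorded end | Class under SAP 9.2.1 | Class with the fix |
|---|---|---|---|
| June 2020, day unknown | 15 June 2020 | TEAE | Pre-treatment |
| 2020, month unknown | 15 June 2020 | TEAE | Pre-treatment |
| June 2020, day unknown | 25 June 2020 | TEAE | TEAE |
| May 2020, day unknown | none | Pre-treatment | Pre-treatment |
| July 2020, day unknown | none | TEAE | TEAE |
| wholly missing | 15 June 2020 | Neither class | Pre-treatment |
| wholly missing | none | Neither class | TEAE |

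The first two rows are AEs that ended five days before the first dose and are still counted as TEAEs. The last two rows have no class.

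**Step 2: can such records arise?**
- AEs are collected from consent, including any pretreatment period (Protocol 10.1.1.1).
- Direct enrollers have a Screening Visit 2 to 21 days before entry, with AE reporting at both visits (Protocol 8.1, 8.2).
- The daily record card captures start and end dates of undesirable events (Protocol section 9), and the rule for repeated AEs uses an outcome date (Protocol 10.1.2.2). An end date can therefore exist.
- Rollover subjects are much less exposed to the first gap. They take their first dose on the evening of the Entry Visit (Protocol 7.2). Their ongoing AEs stay in the feeder-study database unless intensity or seriousness changes (Protocol 8.3).
- The second gap does not depend on a screening window and can affect any group.

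**Step 3: size per affected subject.** Planned numbers are 90 + 7 + 30 = 127 in Japan and 127 + 90 = 217 overall (SAP 2.4). Direct enrollers are 30/217 = 13.8% of the total. If the misassigned AE is a subject's only TEAE, incidence moves by
- 1/30 = 3.3 percentage points among direct enrollers;
- 1/217 = 0.46 percentage points overall.

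The number of such subjects is not stated. Assuming 1 to 5, the overall shift is 0.46 to 5/217 = 2.3 points.

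**The case against.** The strongest reply is that the end-date gap can only over-count TEAEs, which is the cautious direction and matches the SAP's other worst-case conventions. The direction is as stated, but the parallel is incomplete. Those conventions fill in a value that is missing, whereas here a recorded end date is disregarded. The reply also does not cover the wholly missing onset, where the error is an omission.

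A second reply is that such records will be rare. The first gap needs an unknown start day and a known end date inside a short window, in about 30 subjects who are asked about AEs at both visits. The second needs an AE without even a year of onset, despite a prompt at each visit, data checks, queries and a Data Evaluation Meeting before lock. An SAE, or an AE leading to discontinuation, would still be listed (SAP 9.2.2.2, 9.2.2.3). This stands, and it is why the point is small.

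Four stronger readings are tempting, and the documents do not support them:
- *The primary variable is misclassified.* Nothing shows that such an AE exists. The rule can misclassify, and no more can be said.
- *TEAEs admitted on a partial date cannot be placed in later tables.* A reader might infer this from SAP 3.2.2: "Relative day will not be calculated for partial or missing dates". But SAP 9.2.2 works from the onset date: "For by-study period summary tables, TEAEs will be attributed according to the onset date". An AE admitted by the month branch, taken as on or after first dose, falls within Day 1 to 31. That is always inside Month 1-3 (Day 1-90, SAP 3.2.6). It is also in the Evaluation Period unless the subject stops within that month. Year-only onsets, and later months that straddle a boundary, stay ambiguous, but that does not make partial-date TEAEs unusable in general.
- *Interval tables fail to add up because of partial dates.* They would not sum to the overall count with complete dates either. They exclude onsets after the last dose, which the overall tables include (SAP 9.2.2).
- *Most month-only screening AEs are misclassified.* With onset uniform over the screening window, 64% (21-day window) to 95% (2-day window) of them share the calendar month of first dose. That share ignores whether the AE ended before first dose, so it does not measure the error.

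**Conclusion.** The point holds as a gap in the specification. SAP 9.2.1 assigns a wrong class to a partial-onset AE whose recorded end date is before the first BRV dose, and no class to an AE without an onset date. No other section corrects either.

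The consequence is limited. The first gap reaches mainly the roughly 30 direct enrollers, and each subject whose only TEAE is affected moves that group's incidence by 3.3 points. The second could drop an event in any group. The number of affected AEs is not given and is probably small. The study is uncontrolled and descriptive, so no test or error rate is involved. The conclusion assumes that AE end dates reach the analysis database; the documents show that they are recorded but do not show the AE page of the eCRF.

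The amendment is still worth making, because it concerns the primary variable and costs almost nothing.

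**What to change.** Amend SAP 9.2.1 with two sentences:
1. An AE with an incomplete onset that meets the month or year rule is a TEAE unless its recorded end date is before the first BRV dose in EP0085.
2. An AE with a wholly missing onset is a TEAE unless its recorded end date is before the first BRV dose in EP0085.

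This keeps the cautious default wherever the record is silent. As the last column of the table shows, it leaves no test case without a class. The cost is two sentences and a few lines of derivation code, with no new data collection. No imputed onset dates are needed for this purpose.

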### **9.2.2 Summaries of TEAEs**

Pre-treatment AEs will be provided in a subject data listing; no summary of pre-treatment AEs are planned. Summaries will be for TEAEs and will be provided overall by combining Evaluation Period, Down-Titration Period, and Study Drug-Free Period unless otherwise indicated.

The following summary of TEAEs will be provided:

- Incidence of TEAEs – overview (overall and by study periods)

The following summaries of TEAEs will be provided by MedDRA SOC and PT:

- Incidence of TEAE (overall and by study periods)
- Incidence of TEAEs by safety time interval (overall)
- Incidence of TEAEs above reporting threshold of 5% of subjects (overall)
- Incidence of non-serious TEAEs above reporting threshold of 5% of subjects (overall)
- Incidence of TEAEs by maximum intensity (overall and by study periods)
- Incidence of TEAEs by relationship (overall and by study periods)
- Incidence of TEAEs leading to permanent discontinuation of study drug (overall)
- Incidence of treatment-emergent SAE (overall and by study periods)
- Incidence of treatment-emergent SAE by relationship (overall)
- Incidence of fatal TEAEs by relationship (overall)
- Incidence of TEAEs of special interest (overall and by study periods)
- Incidence of TEAEs requiring dose change (overall and by study periods)
- Incidence of TEAEs related to COVID-19 vaccination (overall and by study periods)

For by-study period summary tables, TEAEs will be attributed according to the onset date.

Three-month safety time interval will be used to summarize data up to and including the maximum duration of exposure to BRV. TEAEs which had onset prior to or on the date of the last dose of BRV are included in summaries by 3-month time intervals. A subject is included in a 3-month interval if the subject was receiving BRV at any time during that interval based on their duration of exposure to BRV (eg, a subject with exposure for 91 days is included in the time interval for Months 1-3 and Months 4-6). Summaries of AEs by 3-month intervals will include all subjects who are classified into each time interval as defined above as the denominator and TEAEs reported within the specific time interval according to the onset date as the nominator.

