- Down-Titration Period (up to 4 weeks):

---

- If the subject is discontinuing study drug, the Investigator will first plan an EDV followed by the progressive down-titration of study drug.
- During the Down-Titration Period, the BRV dose may be decreased in steps of a maximum of 50mg/day on a weekly basis. A last down-titration step at 25mg/day for 1 week should be included prior to the 2-week Study Drug-Free Period.
- 2-week Study Drug-Free Period: After completion of the Down-Titration Period, or for those subjects who for extenuating circumstances do not complete a Down-Titration Period, the subject will be required to enter a 2-week Study Drug-Free Period, followed by a Final Visit (FV).

Subjects who will be converted to the commercial BRV product will complete an End of Study Visit without entering the Down-Titration Period or the 2-week Study Drug-Free Period and will not complete an FV.

Visits should occur on the specified Visit/Week. A  $\pm 7$  day window for each specified Visit/Week is allowed, provided the subject has adequate investigational medicinal product (IMP) to sustain the visit window. The end of the study is defined as the date of the last visit of the last subject in the study.

EP0085 will continue until the market approval of BRV, or until the sponsor decides to close the study, whichever comes first. In the event that market approval is not requested or obtained in the participant country, the subject will be able to continue in EP0085 for two years after entering EP0085.

In Japan, EP0085 will continue as a postmarketing clinical study (Phase 4) after the date of approval of BRV for the partial seizure indication.

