### 3.2.6 Monthly time intervals

In terms of the analysis, a month is defined as 30 days and time intervals based on monthly durations are defined as a multiple of 30 days (eg, 12 months is defined as 360 days). The following definitions of 3-month intervals are based on 30-day months where the date of first dose of BRV is Day 1:

Interval	Duration Definition
3-month interval	
Month 1-3	Day 1-90
Month 4-6	Day 91-180
Month 7-9	Day 181-270
Month 10-12	Day 271-360

Subsequent 3-month intervals are defined in a similar manner. Three-month intervals will be used for analyses of efficacy (except for continuously seizure-free) and TEAE summaries.

For the analysis of efficacy outcomes, a subject is included in the analysis of a 3-month interval if the last dose of study drug during the Evaluation Period of EP0085 is equal or

greater than the last day of the 3-month time interval and the seizure diary was completed for at least 1 day during the 3-month interval over the Evaluation Period.

For TEAE summaries, a subject is included in the analysis of a 3-month interval if the last dose of study drug in whole period of EP0085 is equal or greater than the first day of the 3-month time interval (as N for the time interval) and with at least one specified TEAE within the 3-month interval (as n in the summary tables according to the AE onset date).

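### The 3-month TEAE percentages mix fully and partly exposed subjects with no time at risk shown, so their trend over time on BRV cannot be interpreted

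*SAP*

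**What the plan says.** SAP 3.2.6 sets the time scale: "a month is defined as 30 days and time intervals based on monthly durations are defined as a multiple of 30 days". Each 3-month interval is therefore 90 days, counted from the first BRV dose in EP0085.

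The denominator is described twice, consistently. SAP 3.2.6 includes a subject in the interval N if "the last dose of study drug in whole period of EP0085 is equal or greater than the first day of the 3-month time interval". SAP 9.2.2 says "A subject is included in a 3-month interval if the subject was receiving BRV at any time during that interval" and gives an example: "a subject with exposure for 91 days is included in the time interval for Months 1-3 and Months 4-6". By SAP 3.2.1, the last dose includes down-titration.

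The numerator is cut at the last dose: "TEAEs which had onset prior to or on the date of the last dose of BRV are included in summaries by 3-month time intervals".

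SAP 9.1.1 derives exposure time ("Total study medication duration in subject-years will be calculated as the total duration of exposure in days divided by 365.25"), but none of the TEAE summaries in SAP 9.2.2 uses it. SAP 9.2.2.1 adds a general statement that TEAE percentages use the Safety Set as denominator, and does not except the interval tables.

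For efficacy intervals, SAP 3.2.6 sets a stricter rule: dosing in the Evaluation Period must reach the interval's last day.

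**The concern.** A subject who leaves partway through an interval adds a full unit to the denominator, but can add to the numerator only on the days still on drug. If leaving has nothing to do with TEAEs, the percentage is diluted.

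Such departures are built into the design. SAP 2.3 ends the study at market approval or sponsor closure and allows conversion to commercial BRV. Where approval is not requested or obtained, "the subject will be able to continue in EP0085 for two years after entering EP0085". SAP 9.2.2 continues the intervals up to the longest exposure, so the last ones will hold few subjects, many of them partly exposed.

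The primary objective is long-term safety and tolerability, and the primary variable is TEAEs. The interval table is the only planned TEAE summary by time on BRV. A fall in its percentages could be taken for improving tolerability when it reflects only shorter observation.

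**Working it through.** **The SAP's own example.** Interval k covers Days 90(k-1)+1 to 90k. With 91 days of exposure a subject has 90 days in interval 1 and 1 day in interval 2, so is counted in both, as SAP 9.2.2 states. In Months 4-6 that subject weighs the same as one with 90 days.

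**Stopping unrelated to TEAEs.** Assumed inputs, none given in the documents:
- p: true 90-day risk of at least one TEAE under a constant hazard, λ = -ln(1-p)/90.
- f: share of the interval's subjects who end treatment in it, with last doses spread evenly over Days 1 to 90 of the interval (mean 45.5 days at risk).

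Crude percentage = (1-f)·p + f·m, where m is the mean of 1-exp(-λd) over d = 1 to 90. For p = 30%, m = 16.1%. At f = 30% this gives 0.7 × 30% + 0.3 × 16.1% = 25.8%.

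| f | p = 10% | p = 20% | p = 30% | p = 50% |
|---|---|---|---|---|
| 10% | 9.5% (-4.9%) | 19.0% (-4.8%) | 28.6% (-4.6%) | 47.8% (-4.4%) |
| 30% | 8.5% (-14.6%) | 17.1% (-14.3%) | 25.8% (-13.9%) | 43.4% (-13.1%) |
| 50% | 7.6% (-24.3%) | 15.2% (-23.8%) | 23.0% (-23.2%) | 39.1% (-21.9%) |
| 100% | 5.1% (-48.6%) | 10.5% (-47.6%) | 16.1% (-46.5%) | 28.1% (-43.7%) |

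Brackets show the difference relative to p. The extreme in which every ender has only 1 day gives 21.1% for p = 30% and f = 30%, about 30% too low.

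**Stopping caused by TEAEs.** A TEAE that leads to stopping starts on or before the last dose, so it is counted. Let g be the share of enders who stop for a TEAE counted in the interval, and let p now be the background risk in everyone else. Crude percentage = (1-f)·p + f·[g + (1-g)·m]. Setting this equal to p gives g = (p-m)/(1-m), whatever f is: about 5%, 11%, 17% and 30% for p = 10%, 20%, 30% and 50%. Above that, the table exceeds the background risk. For p = 30%, f = 30% and g = 50% it shows 38.4%.

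**Does a rate remove the dilution?** In a simulation of 200,000 subjects with p = 30% and stopping unrelated to TEAEs, the crude percentage was 30.0%, 26.0% and 22.9% at f = 0, 30% and 50%. The first-event rate, with time stopped at first onset, was 144.6, 145.9 and 144.0 per 100 subject-years. The true rate is λ × 365.25 × 100 = 144.7.

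Stopping time at first onset matters. Dividing subjects with a TEAE by all days on drug gives, under full exposure, p × 365.25/90 × 100 = 81, 122 and 203 per 100 subject-years for p = 20%, 30% and 50%, against true rates of 91, 145 and 281.

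**The case against.** A reader might infer that incidence falls artificially in every interval in which many subjects end treatment. The documents do not support that. TEAEs that cause stopping are counted, and the break-even shares above show that modest TEAE-driven stopping cancels or reverses the dilution. Nor does the SAP say that a 1-day subject is at risk for 90 days. Its N is the number of subjects who received BRV in the interval; the equal weight is only implicit in the percentage.

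A large effect at the two-year limit is also tempting to claim. Suppose the 90 planned Chinese subjects all reach that limit and the other 127 stay on BRV throughout the interval, with p = 20%. Crude percentage = [127 × 0.20 + 90 × (1-exp(-λd))]/217, with d the days at risk in the interval.
- Stop at Day 730, no taper: d = 10 in Months 25-27, giving 12.7%.
- Stop at Day 730, 28-day taper: d = 38, giving 15.4%.
- Stop at Week 96, where the visit schedule places Month 24 (about Day 673), with a 28-day taper: last dose Day 701, d = 71 in Months 22-24, giving 18.4%.

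The result depends on the stopping day and the taper. SAP 2.3 plans down-titration for subjects who do not convert to commercial BRV, so the no-taper figure is not the expected case. It is also a dip in one interval, because these subjects leave the next denominator.

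In late intervals the bias is small in absolute terms. If follow-up were spread evenly over 2-6 years (an assumption), Months 49-51, 61-63, 67-69 and 70-72 would hold about 112, 58, 31 and 18 of the 217 subjects. A constant 20% would show as 18.8%, 17.8%, 15.9% and 12.7%, a shortfall of about 1.3 subjects in each. The binomial standard errors, 3.8 to 9.4 percentage points, exceed the gap every time.

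Finally, all summaries are descriptive, N and event counts are shown, and the plan includes exposure categories, disposition by 6-month period and Kaplan-Meier time to discontinuation.

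These points limit the size of the problem but do not remove it. None of the other displays gives days at risk within a 90-day interval; the Kaplan-Meier numbers at risk come at 12-month steps.

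**Conclusion.** The point holds in limited form. Any BRV use puts a subject in the interval denominator, the numerator stops at the last dose, and no TEAE summary is exposure-adjusted. The size of the understatement when stopping is unrelated to TEAEs rests on a constant hazard, evenly spread last doses and assumed values of f. It is minor when 10% or fewer of an interval's subjects end treatment and material from about 30%, which is most plausible at closure, at conversion to commercial BRV, at the two-year limit and in the last intervals. With enough TEAE-driven stopping the sign reverses.

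Since the direction depends on why subjects stop, the crude trend cannot be read as a change in tolerability without time at risk. No test or sample size is affected. This is worth correcting, but it does not invalidate the safety analysis.

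**What to change.** In SAP 9.2.2, with a matching line in 3.2.6, for each 3-month interval:
- Show total subject-years at risk beside N.
- Add subjects with a TEAE per 100 subject-years. Time at risk runs from the interval's first day to the earliest of first onset of that TEAE category in the interval, last dose, or interval end, counting both end days.
- Optionally add an event rate: all events divided by total days to the earlier of last dose and interval end.
- Keep n (%), footnoted as including partly exposed subjects.
- Base any statement about change over time on the rates.
- State that the 9.2.2 denominator, not the Safety Set denominator in 9.2.2.1, governs these tables.

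Copying the efficacy rule and keeping only subjects dosed to the interval's end would be a poor substitute, because it drops the TEAEs that led to discontinuation.

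The cost is SAP wording and two extra columns in one table family; dose and onset dates are already collected. Late-interval figures may look less favourable, and where little time remains the rates will be unstable, which the subject-years column will make visible.
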